5.1. Statistical Hypotheses and Outcome Definitions

1. Our primary hypothesis is that the intervention will result in significantly **lower cumulative incidence of provider-diagnosed AD by age 24 months**.

After two years of follow-up, we will calculate the proportions of children diagnosed with AD by trained primary care providers in the intervention and control arms. Clinicians will be trained in pediatric AD standard diagnosis criteria.⁴ As our primary analysis, we will test the hypothesis that the ratio of the intervention:control proportions, a relative risk (RR) measure, is significantly smaller than 1 with a two-sided test: **RR ≠ 1 vs RR= 1**. This analysis will be conducted in an intention-to-treat (ITT) analysis dataset of all randomized participants with multiple imputation for missing outcomes.

Provider-diagnosed AD, the current gold standard, will be recorded during chart abstraction and referred to as **GS-AD**. The case report form (CRF) includes a question:

Was there a diagnosis of AD (includes eczema, atopic eczema, atopic dermatitis, and neurodermatitis)? with forced choice responses:

- 1, Yes
- 0, No / No documentation
- 2, Not sure / Possible - AD diagnosis is not confirmed

The CRF further elaborates:

To check "Yes", there must be an official diagnosis from a provider. If a provider is considering eczema as a possibility, or if a parent thinks the child has eczema, mark "Not Sure/Possible" and provide verbatim description from the medical record. Choose "Not sure/Possible" if there is some evidence of eczema but no official diagnosis.

All "not sure/possible" records and their explanatory notes will be reviewed by the principal investigator or dermatology physician co-investigators under blinding before the dataset is locked for analysis. Fields describing the presence and date of onset of similar or comorbid conditions-- such as candida of the skin, impetigo, and molluscum--are part of this record. Parent responses to the Childhood Eczema Questionnaire^{5,6} (CEQ) (see item 2c below) will also be available for review during this determination.

After this review, any child with a "Yes" response or adjudicated as probable AD by physician reviewers will be considered to have AD and the outcome variable will be set to equal 1. "No" and "Not sure" responses adjudicated as not probable AD will be considered not AD and the outcome will be set to 0.

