Over the last week, how much has your child having eczema been a problem at BATH TIME?

3, Very much | 2, A lot | 1, A little | 0, Not at all

10. Delayed onset of AD, with age of onset determined by

a) provider-recorded date of first diagnosis retrieved from record review of chart by research coordinator

[Field:] Date (or age of child in months) of first AD diagnosis in the chart

b) parental report of eczema age of onset to the nearest 3 months (based on quarterly contacts)

Note: For interval-censored analysis, these variables will use the date of visit/response and previous visit/response as the end and start of the interval, respectively.

11. Lower mean days of disrupted sleep in the past week for infants reported by parents at 12 and 24 months, taken from the single item (#4) in the IDQoL.

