- a) Mean Patient-Oriented Eczema Measure (POEM) (a) averaged and (b) summed across all items in the ITT dataset.
- b) Mean score on the 30-point Infants' Dermatitis Quality of Life Index (IDQOL) summed across items in the ITT dataset

Age at onset will be tested using either pooled logistic regression or time-to-event methods for interval-censored data. For these analyses, age of onset will be indexed to the quarterly contact when the parent reported a diagnosis or to the closest corresponding age if the first diagnosis date is in the child's medical chart. Although we may not have sufficient sample size to detect an age-dependent treatment effect, it is possible that the greatest protective effects will be observed at early ages. Kaplan-Meier curves or similar visualizations may help to evaluate differences in treatment effect by age of onset.

9. Age of onset to the nearest 3 months determined by

- a) parental report of eczema from quarterly contacts or annual questionnaires
- b) provider-recorded date of first diagnosis retrieved from record review of chart by research coordinator indexed to the nearest quarter of follow-up

Mean days of disrupted sleep will be treated as a **count** variable and tested with a Poisson model similar to those described above.

10. Lower mean days of disrupted sleep in the past week for infants reported by parents at
 - a) 12 months
 - b) 24 months

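### SAP 5.4 dates chart onset to the nearest quarter but parent-reported onset to the reporting contact, and conflicts with the interval rule in 5.1; if the quarter index is used, early cumulative incidence from the chart is overstated

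*SAP*

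**What the plan says.** SAP 5.4 leaves the method open: "Age at onset will be tested using either pooled logistic regression or time-to-event methods for interval-censored data". It then sets the time scale for these analyses. Onset is "indexed to the quarterly contact when the parent reported a diagnosis or to the closest corresponding age if the first diagnosis date is" in the medical chart. Item 9 is headed "Age of onset to the nearest 3 months determined by", a label placed over both sources. Item 9b repeats the chart rule: the date of first diagnosis is "retrieved from record review of chart by research coordinator indexed to the nearest quarter of follow-up".

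SAP 5.1, item 10, is different. The chart source field is "Date (or age of child in months) of first AD diagnosis in the chart", so dating to the month or better is available. The note there says that for interval-censored analysis "these variables will use the date of visit/response and previous visit/response as the end and start of the interval, respectively".

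Protocol 10.4.4 plans discrete time-to-event methods on the child's age in months, not quarters. SAP 5.4 adds that protection may be greatest at early ages and that Kaplan-Meier curves may help to show it. SAP Table 4 lists Kaplan-Meier summaries for onset by both chart and parent report.

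**The concern.** One event can receive three different dates. Take a child with an AD-free visit at 4.0 months and a chart diagnosis at 4.4 months:

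- Nearest quarter (SAP 5.4, chart): 3 months.
- Reporting contact (SAP 5.4, parent): 6 months, because the 3-month contact closes 14 days after 3 months.
- Visit interval (SAP 5.1 note): between 4.0 and 4.4 months.

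The indexed age of 3 lies before the start of the interval that SAP 5.1 would use. The quarter indexing in 5.4 follows directly after both candidate methods are named, so on its face it covers the interval-censored option too, and there it conflicts with 5.1.

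What is at stake is the age-specific picture. Rounding to the nearest quarter credits each quarterly age with diagnoses that had not yet been made. The relative error is largest at the youngest ages, which is where the SAP hopes to look for protection.

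**Working it through.** **Inputs.** Quarterly ages 3, 6, ..., 24 months (SAP 3.4; SAP 5.7 counts 8 quarters). Cumulative incidence 24% in controls and 16.8% with intervention by two years (SAP 2.3). Contact windows of ±14 days, and -4 to +12 weeks at the annual contacts (SAP Table 2). The documents give no distribution of onset age, so every shape below is an assumption.

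**Check of the incidence inputs.** The plan has no figure for onset dating. Its sample size does reproduce from these incidences: [1.960√(2×0.204×0.796) + 0.842√(0.24×0.76 + 0.168×0.832)]² / 0.072² = 490.6, so 491 per arm and 982 in total, as stated.

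**Effect on the curve.** Let F(t) be the true cumulative incidence by age t. Under nearest-quarter indexing every diagnosis up to t + 1.5 months is counted by quarterly age t (before 24 months), so the indexed curve shows F(t + 1.5). Diagnoses indexed forward do no harm at the quarterly ages: one at 5 months indexed to 6 is correctly counted by 6. Only the backdated ones distort the curve, always upward.

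- Uniform onset from 0: the ratio is (t + 1.5)/t, giving 4.5/3 = 1.50, 7.5/6 = 1.25 and 13.5/12 = 1.125.
- Exponential, mean 9 months (the truncation constant cancels): (1 - e^(-4.5/9))/(1 - e^(-3/9)) = 0.3935/0.2835 = 1.39; 0.5654/0.4866 = 1.16; 0.7769/0.7364 = 1.055.

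In absolute terms, with 24% by 24 months and uniform onset, 3.0% becomes 4.5% at 3 months, 6.0% becomes 7.5% at 6 and 12.0% becomes 13.5% at 12. Indexing upward, to the first quarterly age at or after diagnosis, returns the true values.

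**Range over assumed shapes** (indexed/true ratio, and share of chart events dated before diagnosis):

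| Assumed onset | 3 m | 6 m | 12 m | Dated early |
|---|---|---|---|---|
| Uniform 0-27 m | 1.50 | 1.25 | 1.125 | 50% |
| Exponential, mean 9, to 27 m | 1.39 | 1.16 | 1.055 | 39% |
| Uniform 0-24 m | 1.50 | 1.25 | 1.125 | 44% |
| Uniform 2-24 m | 2.50 | 1.38 | 1.15 | 48% |
| Exponential, mean 6, to 24 m | 1.34 | 1.13 | 1.04 | 34% |
| Exponential, mean 12, to 24 m | 1.41 | 1.18 | 1.07 | 40% |
| Visits 0-1 m after each quarterly age | no true events yet | 2.00 | 1.33 | 100% |
| Visits 0-1 m before each quarterly age | 1.00 | 1.00 | 1.00 | 0% |

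For uniform onset on 0-24 months the share is 7 half-quarters × 1.5 / 24 = 10.5/24 = 44%. On 0-27 months the diagnoses after 24 months are added: (10.5 + 3)/27 = 50%.

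**Effect on the arm contrast.** Pooled logistic regression was fitted to expected counts, 491 per arm, with proportional hazards (hazard ratio ln 0.832 / ln 0.76 = 0.670). The odds ratio is 0.666 under both nearest and upward indexing (constant hazard), and 0.660 v 0.662 (front-loaded, scale 6 months). The 12-month RR is 0.687 v 0.685 (constant hazard).

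Now assume an early effect: hazard ratio 0.45 before 6 months, with the later ratio set so that 24-month incidence is still 16.8% v 24%. The 6-month RR moves from 0.46 to 0.52 (constant hazard) or from 0.47 to 0.55 (front-loaded). The overall odds ratio stays at 0.66 or 0.65.

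**The case against.** **The error depends on a method not yet chosen.** The specific note in 5.1 can be read as governing the interval-censored option, leaving the quarter index for pooled logistic regression only. Under that reading the interval-censored analysis does not backdate. This stands as a condition on the point. It does not remove the mismatch between sources, or the backdating in the other option and in the curves.

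**The rule is the same in both arms and the endpoint is secondary.** This stands. The SAP itself says that the sample may not be large enough to detect an age-dependent effect.

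**Parent dating is not clean either.** This also stands. A 12-month contact may be answered up to 12 + 84/30.44 = 14.8 months, and if indexed to 12 it too can precede the diagnosis.

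A reader might also infer several stronger things that the documents do not support:

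- *Diagnoses before six weeks round to month 0 and are lost.* The grid starts at 3 months, so they go to month 3. If they were lost, the 3-month overstatement would vanish.
- *About half of chart diagnoses are backdated.* That is the top of the 34-50% range under smooth onset; clustered visits allow anything from 0 to 100%.
- *Chart and parent onset differ by a full quarter in half of cases.* This ignores the contact windows: a diagnosis at 3.1-3.4 months can be indexed to 3 by both sources.
- *The 12-month incidence endpoint (item 3a) is affected.* Nothing applies the quarter index to it.
- *Adjudicated cases have no onset date.* A child "adjudicated as probable AD by physician reviewers will be considered to have AD" may have no official diagnosis to date. But Protocol 6.3 codes qualified diagnoses as AD and collects symptom onset where recorded, and the full case report form is not in the documents. The question is open.

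**Conclusion.** The point holds as a minor one. SAP 5.4 dates chart and parent onset by different rules, and its wording conflicts with the note in SAP 5.1. If the nearest-quarter index is used, chart-based cumulative incidence is overstated by about 39-50% at 3 months, 16-25% at 6 months and 5.5-12.5% at 12 months, in relative terms, for uniform onset or exponential onset with mean 9 months. Other shapes move these figures, and visits clustered around the quarterly ages could make them zero or much larger.

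The consequence is confined to age-specific incidences and contrasts of a secondary endpoint. The dilution of an early effect rests on the assumed hazard ratio of 0.45 before 6 months; under proportional hazards there is practically none.

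**What to change.** Reconcile SAP 5.1 item 10 with SAP 5.4 and state one rule for both sources:

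- **Interval-censored analysis:** use actual dates, with the interval running from the previous AD-free visit or response (excluded) to the visit or response with the diagnosis (included), as 5.1 already intends.
- **Pooled logistic regression and curves:** index to the first quarterly age at or after the actual diagnosis date (chart) or report date (parent), not the nominal age of the contact. Add a closing category for events after 24 months, because the chart audit runs through 27 months.
- **Censoring:** state how it is indexed, consistently with the events.
- **Adjudicated probable AD:** where no diagnosis date is recorded, use the date of the first qualifying chart note.

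The heading of item 9 should then drop the nearest-3-months label. The cost is SAP wording, plus at most one date field completed from notes the physician reviewers already read. SAP version 3.0 describes chart audits as ongoing and analysis as not begun, so at that version the change could be made before the data were analyzed.

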10.4.4 Analysis of Key Secondary Endpoints

To test the hypothesis that emollient use delays onset of AD, we will compare time to onset using child's age in months with discrete time-to-event methods.⁸⁴ Time to AD onset will be defined in two ways, as (1) parental report of age of eczema onset and (2) age at first diagnosis recorded in patient chart. Censoring will occur at the date of last parental report or last visit recorded in the patient chart. We will also compare the intervention and control groups with respect to conditions and symptoms that include the need for topical therapy, asthma, food allergy symptoms, and dichotomized disease severity measures as binary measures, sleep loss days as counts, and AD severity scores (POEM and IDQOL) as continuous measures. We will test for differences using logistic, Poisson, or linear regression, adjusting for stratification variables. The incidence of adverse events at two years of age will also be compared between the treatment and control groups with a two-tailed chi-square test at the 0.05 level of significance.

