3.1. Level of Statistical Significance

In the primary analysis, use a type I error rate of 0.05. Secondary outcomes will be considered significant at $\alpha=0.05$ and exploratory analyses at $\alpha=0.1$. All tests will be two-tailed.

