Over the last week, on how many days [nights, item 2] has your child's ...

... skin been itchy because of their eczema?

... sleep been disturbed because of their eczema?

... skin been bleeding because of their eczema?

... skin been weeping or oozing clear fluid because of their eczema?

... skin been cracked because of their eczema?

... skin been flaking off because of their eczema?

... skin felt dry or rough because of their eczema?

b) Lower mean score on the 30-point Infants' Dermatitis Quality of Life Index (IDQOL) where higher scores indicate more impairment¹². To score, sum the items below. A missing item will result in a missing response.

Over the last week, HOW SEVERE do you think your child's dermatitis has been? In other words, how red, scaly, inflamed or widespread.

4, Extremely Severe | 3, Severe | 2, Average | 1, Fairly Good | 0, No Eczema

Over the last week, how much has your child been ITCHING AND SCRATCHING?

3, All the time | 2, A lot | 1, A little | 0, None

Over the last week, what has your child's MOOD been?

3, Always crying, extremely difficult | 2, Very fretful | 1, Slightly fretful | 0, Happy

How many nights in the past week would you say your child's sleep was disturbed at night, not including routine feeding? 0-7

Over the last week approximately how much TIME on average has it taken TO GET your child OFF TO SLEEP each night?

3, More than 2 hours | 2, 1 to 2 hours | 1, 15 minutes to 1 hour | 0, 0 to 15 minutes

Over the last week, what was the TOTAL TIME that your child's SLEEP WAS DISTURBED on average each night?

3, 5 hours or more | 2, 3-4 hours | 1, 1-2 hours | 0, Less than 1 hour

Over the last week, has your child's eczema interfered with PLAYING OR SWIMMING?

3, Very much | 2, A lot | 1, A little | 0, Not at all

Over the last week, has your child's eczema interfered with them TAKING PART IN or ENJOYING OTHER FAMILY ACTIVITIES?

3, Very much | 2, A lot | 1, A little | 0, Not at all

Over the last week, have there been problems with your child at MEALTIMES because of the eczema?

3, Very much | 2, A lot | 1, A little | 0, Not at all

Over the last week, have there been problems with your child caused by the TREATMENT?

3, Very much | 2, A lot | 1, A little | 0, Not at all

Over the last week, has your child's eczema meant that DRESSING AND UNDRESSING the child has been UNCOMFORTABLE?

3, Very much | 2, A lot | 1, A little | 0, Not at all

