5.3. Analysis of Primary Endpoint

For the primary analysis, we contrast the risk of diagnosed atopic dermatitis (AD) by two years of age for the intervention versus control groups under an intention-to-treat (ITT) assumption, analyzing all subjects according to the group to which they were allocated regardless of adherence or group crossover, and imputing missing outcome values using multiple imputation methods. The measure of interest is the ratio of the intervention:control proportions, a relative risk (RR) measure. If emollient use prevents AD, the RR will be significantly smaller than 1.

Estimation of the relative risk will be by log-binomial regression using a generalized linear model with a log link and binomial distribution. A binary indicator variable will represent assigned **study arm** (intervention=1, control=0). The exponentiated coefficient of this variable, $\exp(\beta_1)$, estimates RR. We will test $\beta_1 \neq 0$ at the 0.05 level of significance. If $p < 0.05$, we will consider RR significantly different from 1, meaning that there is strong evidence for the effect of emollient use on AD in very young children.

Stratification variables will also be included in the model to avoid bias in estimates of effects and standard errors. The stratification variables are **family history of atopy in a first-degree relative** and **recruiting clinic**, which will be included as a **random effect**. Because there are 45 recruiting

clinics in the study, clinic cannot be modelled as a fixed effect without losing statistical efficiency. No other baseline characteristics will be included.

Equation 1

$$\log(p[AD_{ij}]) = \beta_0 + \beta_1 Arm_{ij} + \beta_2 FamHx_{ij} + b_j$$

In this model, the variable *Arm* represents assigned **study arm** (intervention=1, control=0) for participant *i* recruited from clinic *j*. The variable *FamHx* represents family history of atopy in a first-degree relative (1/0). The term b_j is a random intercept for the primary care clinics where participants were recruited. The exponentiated intercept coefficient ($\exp(\beta_0)$) represents the cumulative prevalence of AD in the control arm, while $\exp(\beta_1)$ estimates RR.

Alternative strategies could be used to overcome convergence issues. If this model fails to converge, alternatives include substituting a Poisson model with robust variance estimates, providing starting values for estimation in the statistical software, or using an alternative algorithm.

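### SAP 5.4 does not say which standard errors the Poisson test of disrupted nights uses; with model-based ones the true error rate could lie between about 2% and 29%

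*SAP*

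**What the plan says.** The endpoint is item 11 of SAP 5.1: "Lower mean days of disrupted sleep in the past week for infants reported by parents at 12 and 24 months". The value is to come from item 4 of the IDQOL, which reads "How many nights in the past week would you say your child's sleep was disturbed at night, not including routine feeding? 0-7".

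SAP 5.4 treats it as a count, "tested with a Poisson model similar to those described above", separately at 12 and 24 months. Protocol 10.4.4 lists sleep-loss days as counts and says "We will test for differences using logistic, Poisson, or linear regression, adjusting for stratification variables". Neither section names a variance estimator, a dispersion check or an overdispersed count model for this endpoint.

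The only Poisson model described earlier in the SAP is in 5.3, where "substituting a Poisson model with robust variance estimates" is one of several options if the primary log-binomial model does not converge.

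On the test level, SAP 3.1 says "Secondary outcomes will be considered significant at" 0.05 and "All tests will be two-tailed". SAP 3.2 plans no numerical adjustment for multiple secondary tests.

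**The concern.** A Poisson model takes the variance to equal the mean. Disturbed nights within one infant's week are unlikely to be independent: a poor sleeper tends to have several bad nights and a good sleeper none. That correlation raises the variance. If it exceeds the mean, model-based standard errors are too small, confidence intervals are too narrow, and a nominal 5% test rejects too often. If it falls below the mean, the test is conservative and loses power. The plan does not say which standard error will be used, so the properties of these two tests are not fixed in advance.

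A second point concerns where the number comes from. The SAP 2.7 schema asks the IDQOL only if the infant develops AD. The same schema has a separate sleep-loss row for all infants, and Table 4 lists disrupted nights under the ITT population. Read literally, item 11 would compare arms among AD cases only, a group defined after randomisation.

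**Working it through.** **Inputs from the documents.** Range 0 to 7; two time points; two-sided 0.05; 1:1 allocation; 491 evaluable infants per arm (SAP 2.3); 45 clinics as a random intercept and family history as a covariate (SAP 5.3).

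**Not in the documents.** The mean, variance or distribution of disrupted nights. These are assumed below over a range.

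**Step 1: the plan's own figures.** For 24% against 16.8%, two-sided 0.05 and 80% power, the pooled-variance formula is

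n = [1.96 √(2 × 0.204 × 0.796) + 0.8416 √(0.24 × 0.76 + 0.168 × 0.832)]² / 0.072² = 490.5, so 491 per arm and 982 in total, as stated.

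This serves only as the simulation size; the error rate below hardly depends on it. For the sleep endpoint the plan gives no figure except the nominal 5%.

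**Step 2: error rate with model-based standard errors.** With φ = variance/mean, the Wald statistic has standard deviation √φ under the null, so

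type I error = 2 × [1 − Φ(1.96/√φ)].

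- φ = 0.7: 1.9%
- φ = 1.0: 5.0%, the nominal level
- φ = 1.5: 11.0%
- φ = 2.0: 16.6%
- φ = 2.5: 21.5%
- φ = 3.0: 25.8%

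**Step 3: when φ exceeds 1.** For a count out of 7 nights with mean m and between-night correlation ρ,

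φ = (1 − m/7)(1 + 6ρ).

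The first factor is the effect of the cap and is always below 1. Setting φ = 1 gives ρ = [1/(1 − m/7) − 1]/6, which is 0.03 at m = 1.05, 0.07 at m = 2.1 and 0.17 at m = 3.5.

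Differences between infants alone can reach this. Take the plan's 24% control incidence of AD, assume means of 3.5 nights with AD and 1.0 without, and let nights be independent within each group:

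- overall mean: 0.24 × 3.5 + 0.76 × 1.0 = 1.60
- variance: (0.24 × 1.75 + 0.76 × 0.857) + 0.24 × 0.76 × 2.5² = 1.07 + 1.14 = 2.21
- φ = 2.21/1.60 = 1.38, for an error of about 9.5%

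The two means are illustrative only.

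**Step 4: simulation.** 20,000 null trials per scenario, 491 per arm. Nine of the 14 scenarios run:

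| Assumed distribution on 0–7 | Mean | φ | Model-based | Robust |
|---|---|---|---|---|
| Independent nights, p = 0.30 | 2.10 | 0.70 | 1.9% | 5.0% |
| Beta-binomial, ρ = 0.1 | 3.50 | 0.80 | 2.9% | 5.1% |
| Independent nights, p = 0.15 | 1.05 | 0.85 | 3.4% | 5.0% |
| Beta-binomial, ρ = 0.1 | 2.10 | 1.12 | 6.5% | 5.0% |
| Uniform 0–7 | 3.50 | 1.50 | 11.1% | 5.3% |
| 50% extra zeros, else p = 0.30 | 1.05 | 1.75 | 14.1% | 5.1% |
| Beta-binomial, ρ = 0.3 | 2.10 | 1.96 | 16.0% | 4.7% |
| 60% zeros, long tail | 1.16 | 3.00 | 25.1% | 5.1% |
| Beta-binomial, ρ = 0.5 | 1.05 | 3.40 | 28.9% | 5.0% |

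Over all 14, model-based standard errors gave 1.9% to 28.9% and robust ones 4.7% to 5.3%.

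**Step 5: does the clinic random intercept repair it?** A random-intercept Poisson model with 45 clinics, family history and 982 infants was fitted to 400 null trials in each of four scenarios. It gave 3.5% (independent nights, p = 0.15), 16.5% (mean 2.1, ρ = 0.3), 10.5% (50% extra zeros) and 26.5% (60% zeros, long tail), with simulation error of about 1 to 2 percentage points. It does not: the extra variation lies between infants, not between clinics.

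**The case against.** A reader might infer that the plan commits to a plain Poisson model, that its standard errors will be too small and that false positives will run well above 5%. The documents do not support that.

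- **The wording is open.** The only Poisson model described earlier carries robust variance, so the reference back in SAP 5.4 could import it. The other reading is more natural. For continuous outcomes the same section uses similar phrasing for model structure and then states the standard-error remedy separately (bootstrap if non-normal); nothing of that kind is added for the count. Both readings remain possible.
- **The dispersion is unknown.** No document says that many infants score 0 or some score 7. With nearly independent nights the test is conservative.
- **The 0–7 bound is not the cause.** A cap lowers the variance. Only correlation between nights, or differences between infants, raises it above the mean.
- **Robust intervals need not be wider.** They widen under overdispersion and narrow under underdispersion.
- **Item 11 need not mean an AD-only analysis.** The all-infant schedule row and the ITT listing in Table 4 point the other way. This is a conflict to reconcile, not a settled restriction.

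It is also fair that Table 4 will report the distribution, mean and SD by arm, so readers could see any overdispersion, and that SAP 5.10 leaves room for further sensitivity analyses before unblinding. Neither fixes the test in advance. What stands is that the plan allows two readings, and one of them gives a test whose size is not controlled.

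**Conclusion.** The concern holds as an unspecified standard error, not as a demonstrated error. If model-based Poisson standard errors are used, the type I error of each sleep test lies between about 2% and 29% over the distributions tried. Overdispersion is the likelier direction because so little between-night correlation is needed, but that is a judgement; the documents contain no data on it. If robust variance is meant, the error is close to 5% and only the wording needs attention.

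The result assumes a Wald test and numbers of respondents near 491 per arm. The robust error rates come from a two-arm comparison without clinic or covariates. Two secondary tests, at 12 and 24 months, are affected. The primary analysis is not. The change is worth making because it is nearly free and protects against error in both directions.

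**What to change.** In SAP 5.4, state that the disrupted-nights models at 12 and 24 months use a log-link Poisson mean model with robust (sandwich) standard errors, with the ratio of mean nights as the estimate, and say how clinic enters the model and the variance. A negative binomial model is a less clean substitute because it cannot represent underdispersion. A standard logit binomial-out-of-seven model would change the estimate to an odds ratio.

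In SAP 5.1 item 11, name the all-infant sleep item as the source and the ITT population as the analysis set, in line with the schema in 2.7 and Table 4.

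The cost is two sentences and one software option. There is no new data collection and no change to the estimate of interest. SAP 3.0 describes itself as written before analysis, so the edit fits within its own revision process.
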